## **9.7 Treatment Compliance**

Site personnel will maintain a record of all IMP dispensed to each subject.

For this trial, treatment compliance is defined as completion of 100% of scheduled doses, because the study drug administration is under direct control of the Investigator or designee.

## **9.8 Non-Investigational Medicinal Product (non-IMP)**

The radioligand [F]-IMA601 (non-IMP) will be prepared by the PET site.

Product name: [F]-IMA601 (also known as [F]OGA1)

Dosage form: Solution

Effective dose: maximum 2.46 mSv each PET scan, as it includes components from PET (2.1 mSv) and CT scans (0.36 mSv)

Injected activity: Will not exceed 100 MBq for each PET scan

Route of administration: intravenous bolus

Manufacturer/source of procurement: PET site§

§ cGMP grade precursor will be procured from an external commercial source

## **9.9 Storage and Return of Study Drug**

Upon receipt of the study drugs, the responsible pharmacist will inspect all study drugs for completeness. Subsequently, he/she must immediately return the enclosed acknowledgement of receipt form; duly completed and signed (the date of receipt must be noted).

The pharmacist is responsible for storage of the study drug at the study site in an appropriate lockable room at refrigerated temperature (2-8 °C). The drug will be stored according to the instructions provided by Asceneuron SA. Only the pharmacist or his/her assistant, who are otherwise not involved in the study, will handle the study drug.

A dispensing record (or similar document) as well as a Drug Accountability Record must be kept current and should contain the following information:

- Subject number for whom the drug was prepared

- Initials and date of the person who prepared the study drug
- Dates on which drug was prepared and quantity of the drug prepared
- The inventory must be available for inspection by the monitor

After sponsor confirmation, all unused investigational material (drugs and packaging) must be destroyed by the site on termination of the study and after a drug accountability check by the monitor, listing the following:

- All ASN51 administered
- All unused ASN51
- All ASN51 destructed by the site

Alternatively, upon request of Asceneuron SA, the pharmacist may send back the unused investigational drug. The pharmacist will be responsible for the inventory and accountability of all Clinical Trial Material, exercising accepted pharmaceutical practices. An accurate, timely record of the Clinical Trial Material will be maintained. Only after completion of the study, the Clinical Trial Material and the inventory will be available for inspection by the designated representatives of Asceneuron SA upon request. The original dispensing records and Drug Accountability Record are considered as source data and will be archived at the site.

## **9.10 Diet, Activities, and Other Restrictions**

### **9.10.1 Concomitant Medications**

Use of prescription or non-prescription drugs, vitamins, herbal, and dietary supplements (including St John's Wort) within 7 days (or 28 days if the drug is a potential hepatic enzyme inducer) or 5 half-lives (whichever is longer) prior to the first dose of study tracer medication and until the Follow-up visit.

The use of other types of concomitant medication is not allowed from 1 week prior to the first dose of study tracer medication until the Follow-up, except for paracetamol (at most 2g /day) or medication that is required for the treatment of AEs. If concomitant medication is needed during the study, this medication must be recorded on the eCRF, stating its generic name, time of administration, dose, route and duration, as well as the reason for administration.

Subjects who received a COVID-19 vaccination within two weeks of screening will be excluded from the study. Concomitant administration of a COVID-19 vaccination during the course of study participation will not be permitted.

An exception applies to the use of hormonal contraceptives as follows:

- combined (estrogen and progestogen containing) hormonal contraception associated with inhibition of ovulation:
  - intravaginal

- transdermal
- progestogen-only hormonal contraception associated with inhibition of ovulation:
  - injectable
  - implantable
- intrauterine hormone-releasing system (IUS)

#### **9.10.2 Caffeine**

Subjects will abstain from ingesting caffeine- or xanthine- containing products (e.g. coffee, tea, cola drinks and chocolate) from 24 hours prior to first tracer dose administration until 72 hours after each study drug administration.

#### **9.10.3 Alcohol**

Subjects will abstain from alcohol for 48 hours prior to first tracer dose administration until the follow up visit.

#### **9.10.4 Physical Activities**

Subjects will abstain from strenuous exercise from 7 days prior to first tracer dose administration until the last follow up visit. Subjects may participate in light recreational activities during the study.

#### **9.10.5 Dietary Aspects**

Consumption of Seville oranges or grapefruit (or their juices) is not allowed from 7 days prior to the first dose of the tracer medication until 72 hours after the last study drug administration.

#### **9.10.6 Smoking**

Use of any tobacco- or nicotine-containing product is prohibited from 1 week prior to first tracer administration until 72 hours after the last study drug administration.

#### **9.10.7 Definitions of Women of child-bearing potential**

A woman is considered of childbearing potential (WOCBP), i.e., fertile, following menarche and until becoming post-menopausal unless permanently sterile. Permanent sterilisation methods include hysterectomy, bilateral salpingectomy and bilateral oophorectomy.

### **10.0 STUDY PROCEDURES AND ASSESSMENTS**

The Schedule of Events, including allowed visit windows, assessments, and procedures to be conducted at each visit are detailed in Table 1. Guidelines for study procedures and assessments are discussed briefly in the following sections.

## 10.1 Structural MRI

Structural MRI acquisition will be performed at [REDACTED] and will consist of a structural scanning protocol. MRI scans will be evaluated by a radiologist to exclude any subjects with major pathology or abnormalities. A radiologist's report will be provided for each MRI scan to the Investigator at [REDACTED]

## 10.2 PET scan

Dynamic PET scans will be performed at [REDACTED] using a Siemens Biograph 6 PET/computed tomography (CT) scanner (Siemens Healthcare, Erlangen, Germany). The subjects will be placed in the PET scanner during the scan. A low dose CT scan will be performed to correct for the attenuation of emitted radiation. Subjects will then receive an intravenous bolus injection of up to 100 MBq of the [F]-IMA601 radioligand. Dynamic emission data will be recorded for up to about 90 min after injection of the radioligand.

## 10.3 Clinical Safety Assessments

Assessments to characterize safety and tolerability of ASN51 are described below; associated planned analyses are described [Section 12.7](#).

### 10.3.1 Informed Consent

Informed consent will be obtained as outlined in [Section 13.1.2](#).

### 10.3.2 Medical History and Demographics

Medical history includes active conditions, and any medical illnesses, diagnoses, and surgeries considered clinically relevant by the Investigator.

Demographic information (year of birth, sex, race, ethnicity) will be recorded at Screening (as allowed by local regulations).

### 10.3.3 FSH tests

Serum FSH tests will be done using a chemiluminescent immunoassay method.

### 10.3.4 Drugs of abuse, urine alcohol and cotinine tests

Urine will be tested for drugs of abuse, urine alcohol and cotinine according to the laboratory's SOP. Tests will include: amphetamines, cocaine, opiates, cannabis, barbiturates, benzodiazepines, and cotinine

### **10.3.5 Weight and Height**

Weight (measured in kilograms) and height (in meters) will be measured and recorded as noted in the Schedule of Events. Subjects may remain in clothes (without shoes). A standing height will be measured and recorded using a stadiometer at the Screening Visit only.

### **10.3.6 Physical and Neurological Examination**

Complete physical examinations will be performed by a licensed professional at Screening, at follow-up, and at early termination, when applicable. A complete physical examination includes general appearance; head, eyes, ears, nose, and throat; and cardiovascular, dermatologic, respiratory, gastrointestinal, musculoskeletal, and neurologic systems.

All other indicated physical examinations should be symptom-directed, and include neurological assessment of cranial nerves, motor, sensation, coordination, reflexes, and gait.

Findings will be recorded as normal/abnormal for each parameter with additional description as indicated.

### **10.3.7 Vital Signs**

Vital signs include systolic and diastolic blood pressure (mm Hg), heart rate (beats per minute), respiration rate (breaths per minute), and temperature (°C; tympanic). Measurements will be obtained as noted in the Schedule of Events. At screening, obtain triplicate blood pressure measurements (5-minute intervals) while the subject is seated; use the average to assess eligibility. During the study, blood pressure may be assessed as single recording in seated position after a rest of 5 minutes.

### **10.3.8 Electrocardiogram**

Routine single 12-lead ECGs will be performed after the subject has rested for a minimum of 10 minutes. All ECGs will be stored digitally. ECGs may be repeated once to rule out a technical error with new lead placement; only the values of the second recording will be entered into the data base. Perform additional assessments as clinically indicated.

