17. **12-Lead ECG:** During the period of residence, ECGs will be recorded at the timepoints indicated. Assessments will be done at screening visit 1, Day -1 of imaging session 1, and pre-dose on Day 1 in imaging sessions 2 and 3, and at the follow-up visit. Single recordings will be done at all time points. Recordings should be made with subjects in a supine position, after resting for 10 min. Additional unscheduled assessments may be done at the discretion of the Investigator.
18. **PK Sampling:** Plasma samples for assay of the ASN51 will be collected pre-dose and at 0.25, 0.5, 1, 1.5, 2, 3, 4, 6, 8, 12, 16, 24, 36, 48, and 72 h post-dose. Samples scheduled immediately before the PET scan should be taken as close as possible to the planned start of the PET scan samples scheduled for the end of the PET scan should be taken as soon as possible after the PET scan is finished; and samples scheduled during the PET scan should be taken either before or after the PET scan, as close to the scheduled timepoint as possible.
19. Hematology, biochemistry, coagulation, and urinalysis to be taken 72 h post-dose in sessions 2 and 3.
20. **Timing of Assessments:** If more than one assessment is foreseen for a timepoint, PET procedures prevail. All assessments should be staggered in the same order throughout the study with the PK sampling point closest to the scheduled timepoint.

3.0	TABLE OF CONTENTS	
1.0	TITLE PAGE	1
2.0	STUDY SYNOPSIS	4
3.0	TABLE OF CONTENTS	14
4.0	LIST OF ABBREVIATIONS AND DEFINITION OF TERMS	18
5.0	INTRODUCTION AND RATIONALE	21
5.1	Background: O-GlcNAcylation and Protein Aggregation in Neurodegenerative Disease	22
5.2	ASN51 Mechanism of Action and Rationale in Alzheimer's Disease	23
5.3	Nonclinical Studies	25
5.4	Clinical Experience	27
5.5	Summary of Overall Risks and Potential Benefits	27
6.0	OBJECTIVES	28
7.0	INVESTIGATIONAL PLAN	29
7.1	Study Design	29
7.2	Treatment Assignment and Blinding	30
7.2.1	Number of Subjects	30
7.2.2	Method of Assigning Subject Numbers to Treatment Groups	30
7.2.3	Blinding	31
7.2.4	Unblinding	31
7.3	Sites	31
7.4	Study Duration	31
7.5	Study Safety Oversight	31
7.5.1	Safety Review Committee	31
7.5.2	Stopping Criteria Based on Urgent Safety Events	31
7.5.3	Criteria for Dose Level Selection	32
7.6	Subject Discontinuation	32
7.6.1	Removal of Subjects	32
7.6.2	Early Termination Procedure	33

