## 7.0 INVESTIGATIONAL PLAN

### 7.1 Study Design

This is an open-label, adaptive-design PET study to investigate the occupancy of O-GlcNAcase by ASN51 after single oral doses in healthy adult male and female subjects (aged 25-55 years, inclusive). The study schema is depicted in [Figure 2](#).

**Figure 2:** Phase 1a ASN51-102 Study Schema

Up to 10 subjects will be enrolled. Each subject will have up to 3 imaging sessions, with one scan in each session. In the first imaging session, subjects will have 240 ml of water followed by a baseline PET scan approximately 2 h later. In the second and third imaging sessions, subjects will receive a single oral dose of ASN51 with 240 ml of water, followed by an on-treatment PET scan. Safety and pharmacokinetic data of the SAD study ASN51-101 will be assessed by the SRC prior to the dosing of the first subject(s) to determine the first dose level to be administered in session 2 after the baseline session 1 and the timing of the PET scans in relation to the study drug administration time. At most 2 subjects will be dosed on the same study day. For subsequent sessions, the dose level and the time of the PET scan in all imaging session 2 and 3 will be determined after review of the results from the first on-treatment PET scan, including the PK data. Subjects will receive an intravenous dose of the radiolabelled tracer, [F]-IMA601, at the start of each PET scan.

This study will have an adaptive design: to adequately evaluate the exposure versus receptor occupancy (RO) relationship, various doses of ASN51 of up to 85% of the highest well-tolerated dose level in the preceding SAD study ASN51-101, and the timing of on-treatment PET scans may

be altered based on emerging data or study logistical requirements. On-treatment PET scans may be scheduled up to 48 h post-dose.

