11.2 Derived and transformed data

Baseline will be considered to be the latest value obtained before study drug administration (eg Day 1, pre-dose; or Day -1 if not recorded at pre-dose; or screening if not recorded at pre-dose or on Day -1).

Laboratory data will be reported in standard units. Out-of-range laboratory tests may be repeated. If a test is out of-range at baseline and repeated before dosing, the latest repeat value before dosing will be used as baseline. However, if a test is out-of-range and repeated at any other time during the study, the out-of-range value (not the repeat value) will be included in statistical summaries.

TriPLICATE vital sign measurements will be made at screening and the mean of the three measurements for each subject will be used for analysis.

The PK parameters to be derived are given in Appendix A: Pharmacokinetic Analysis.

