13.6.2 ECG

QT interval data will be presented using Fridericia's (QTcF) and Bazett (QTcB) corrections.

ECG variables will be summarised by treatment and time point.

QTcF and QTcB values > 450 msec, PR interval shortening < 120 msec, and PR interval prolongation > 220 msec will be listed by treatment and timepoint and summarised. A separate listing of ECG findings classified as abnormal by the investigator will also be provided.

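### A repeat ECG replaces the first reading in the database even when no technical error is found, so a valid borderline QTc or PR value can drop out of the outlier tables

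*Protocol*

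**What the plan says.** **The repeat rule.** Protocol 10.3.8 states that "ECGs may be repeated once to rule out a technical error with new lead placement", and then that "only the values of the second recording will be entered into the data base". Replacement does not depend on an error being found. The section does not say what prompts a repeat, and it does not ask for the first value or the reason to be captured. It also says "All ECGs will be stored digitally".

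**The schedule.** Protocol Table 1, note 17, has no replicates: "Single recordings will be done at all time points". ECGs fall at screening, on Day -1 of session 1, and "pre-dose on Day 1 in imaging sessions 2 and 3, and at the follow-up visit".

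**The outputs.** SAP 13.6.2 lists and summarises "QTcF and QTcB values > 450 msec", together with PR below 120 and above 220 msec. Protocol 12.7 adds listings by QTc band and by band of change from baseline.

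**Other repeat rules.** The SAP has none for ECGs. Section 11.2 covers repeated laboratory tests in two parts. For an out-of-range value before dosing, the latest repeat becomes the baseline. At any other time, "the out-of-range value (not the repeat value) will be included in statistical summaries".

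**The concern.** The repeat is there to find out whether the first tracing was faulty. Once that is known, the natural rule is to discard the first value if it was faulty and keep it if it was not. The protocol discards it in both cases.

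If staff tend to repeat an ECG because a value looks abnormal, the first reading has been selected for being extreme, and the second will on average lie closer to the subject's usual value. Keeping only the second then removes some valid readings above the threshold. With single recordings, no replicate stands in for the lost one. The SAP promises complete listings of the data collected, but a value that was never entered cannot appear in them.

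At stake is the completeness of a small set of safety outputs: SAP Table 14.3.7.2, Listing 16.2.9.3 and the protocol 12.7 bands. After baseline, ECG and laboratory repeats would also be treated in opposite ways within one report, with no reason given.

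**Working it through.** The plan gives no figure on this point, so there is none to reproduce. The QTc means and SDs below are assumptions.

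**1. How many recordings are exposed.** Protocol 7.1: "Up to 10 subjects will be enrolled".
- Scheduled ECGs: 5 per subject × 10 subjects = at most 50.
- After a first ASN51 dose (pre-dose session 3 and follow-up): 2 × 10 = at most 20.

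**2. Effect for a subject with a given true QTc.** Let p = 1 − Φ((450 − μ)/SD) be the probability that one recording exceeds 450 ms, with independent errors in the two recordings. If the first value is kept, the flag probability is p. If every first value above 450 ms is repeated and only the second is entered, it is p × p, a relative loss of 1 − p. If repeats depend on trace quality alone, it remains p and the expected loss is zero.

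With SD 8 ms:

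| True QTc (ms) | First kept (p) | Second only (p²) | Relative loss |
|---|---|---|---|
| 440 | 0.106 | 0.011 | 89% |
| 445 | 0.266 | 0.071 | 73% |
| 450 | 0.500 | 0.250 | 50% |
| 455 | 0.734 | 0.539 | 27% |
| 460 | 0.894 | 0.800 | 11% |
| 470 | 0.994 | 0.988 | 1% |

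Over SD 5–10 ms, the loss at 470 ms is 0–2%, and at 440 ms it is 84–98%.

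**3. Effect over the trial.** Assume mean QTcF m, between-subject SD 15, within-subject SD w, no drug effect, no technical error, and a repeat for every first value above 450 ms.
- Total SD = √(15² + w²): 17.0 for w = 8, and 19.2 for w = 12.
- p₁ = P(first > 450) = 1 − Φ((450 − m)/total SD).
- p₁₁ = P(both > 450) = ∫ φ(x) [1 − Φ((450 − m − 15x)/w)]² dx.
- Share replaced by a value at or below 450 ms = 1 − p₁₁/p₁.
- Expected lost flags = 20 × p₁ × share replaced.

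| m | w | p₁ | Share replaced | Mean fall (ms) | First values > 450 in 20 | Lost flags |
|---|---|---|---|---|---|---|
| 415 | 8 | 0.0198 | 0.605 | 9 | 0.40 | 0.24 |
| 415 | 12 | 0.0342 | 0.718 | 17 | 0.68 | 0.49 |
| 420 | 8 | 0.0388 | 0.552 | 8 | 0.78 | 0.43 |
| 420 | 12 | 0.0592 | 0.665 | 15 | 1.18 | 0.79 |

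The conditional share is large (55–72%), but the expected count is below one flag in the whole trial.

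**4. Where the laboratory rule conflicts.** Screening, Day -1 and pre-dose session 2 precede any ASN51. For a pre-dose baseline, SAP 11.2 itself takes the latest repeat, which is the same direction as the ECG rule. The conflict is therefore confined to the two later recordings. If pre-dose session 3 counts as a baseline for its own session, only follow-up remains: at most 10 recordings, or 0.24/2 = 0.12 to 0.79/2 = 0.40 lost flags.

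**The case against.** The case for leaving the rule alone is fairly strong.

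- **Purpose.** The repeat is limited to one, with new lead placement, to deal with suspected artefact. Replacing an artefact is correct, and no systematic bias follows if trace quality is the trigger. This stands. However, the text also replaces the first value when no artefact is found, and nothing restricts the trigger to trace quality.
- **The tracing survives.** ECGs are stored digitally, so a reader who infers that the first reading is destroyed goes too far. It is missing from the analysis database, not from the source. The tables and listings are still built without it.
- **Other routes.** Additional ECGs may be done when clinically indicated, and SAP 11.1 lists data from unscheduled time points. Clinically significant changes can be recorded as adverse events. These routes help with a clinically important abnormality, but they do not restore a borderline value to the outlier tables.
- **Sustained prolongation reappears.** This stands: at a true QTc of 470 ms the loss is 0–2%.
- **Small reach.** This also stands. A reader might infer that the rule distorts the concentration–QT regression in protocol 12.7. It cannot do so through scheduled data, because that model leaves out pre-dose and follow-up ECGs and the remaining scheduled ECGs precede any drug. The lack of any scheduled ECG between dosing and discharge limits QTc detection more than the repeat rule does.

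**Conclusion.** The point holds as a minor one. Replacement is not conditional on a documented fault, and the SAP does not say how ECG repeats are handled. Following the plan can therefore drop a valid abnormal reading from the QTc and PR outputs. The readings at risk are borderline or transient ones.

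The loss is a conditional risk. A reader might infer that QTc abnormalities will be under-reported, but the documents give no trigger, repeat rate or QTc variability to support that. The estimate of 0.2–0.8 lost QTcF flags over at most 20 recordings rests on the assumed means and SDs and on every value above 450 ms being repeated. It ignores the QTcF entry limits (exclusion criterion 19), which would probably make high values rarer. It does not cover QTcB or PR.

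Nor can it be said that the change-from-baseline bands would lean towards normal throughout. If a high baseline reading is replaced by a lower repeat, the change from baseline rises. Only post-baseline replacement of a high value lowers it.

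**What to change.** Amend protocol 10.3.8 and add a matching sentence to SAP 11.2:

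- Enter both recordings in the database with the reason for the repeat.
- List both and flag the one analysed.
- After baseline, analyse the first recording unless a technical fault, such as lead placement or artefact, is documented for it. Genuine artefacts are still replaced, and ECGs then follow the same direction as the post-baseline laboratory rule.
- For the pre-dose baseline, state the rule consistently with SAP 11.2, that is, the latest value before dosing. Say whether the session 3 pre-dose ECG counts as a baseline for this purpose.

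The cost is one extra eCRF record per repeat and one sentence in each document. The stored tracings make it feasible to enter first readings.

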#### **10.3.8.1 ECG Parameters**

ECG Parameters include PR interval, QRS duration, QT interval, QTcB, and QTc-Fredericia's correction (QTcF). ECGs will be interpreted as normal, abnormal clinically not significant (ncs), or abnormal-clinically significant (cs).

### **10.3.9 Prior and Concomitant Medications**

Investigators may prescribe any concomitant medications or treatments deemed necessary to provide adequate supportive care.

All concomitant medication and concurrent therapies will be documented at Screening and at all subsequent visits. Medications (investigational, prescription, over-the-counter, and herbal) and nutritional supplements taken during the 30 days prior to Day 1 of imaging session 1 will be reviewed and recorded as prior medications. Change in concomitant medication since the previous visit will be recorded. Dose, route, unit frequency of administration, and indication for administration and dates of medication will be captured.

If subject is taking high dose biotin supplements (found in multivitamins, biotin supplements, and supplements for hair, skin, and nail growth), site personnel is to advise on the potential for laboratory test interference with certain safety labs.

